There is evidence that strength training is effective in improving the ROM (Afonso et al., 2021). Moreover, a diminished ROM is associated with muscle weakness. The lumbar flexibility is assessed with the help of a goniometer built into the ILEX machine and the sit-and-reach test before, after 6 sessions and 12 sessions of resistance training to control its association with the muscle strength growth. Participants are seated in the ILEX machine in a semi-sitting position with the feet placed on a footrest and the thoracal back leaned against a squared restrained. Restrain belts are secured around the pelvis and shoulders. The movement arm is deblocked and the participants are advised to move dynamically backwards and forwards as far as possible. Three repetitions are done, and peak flexion and extension are registered electronically. Additionally, the combined flexibility of the M. erector spinae and hamstrings is measured using the sit-and-reach test. The sit-and-reach test is probably the most widely used lineal measure of flexibility and it is a simple, easy to administer test with requiring minimal skills. The participant is seated in front of the test box, keeping the knees fully extended and the feet dorsiflexed against the foot-support. The participant is moving actively, slowly forward, bringing the body to the pain-free limit. The participant's hands move the block along the scale until the movement is terminated because the participant can go no farther. The final position is held with an isometric contraction for 2 seconds, and the distance is read on the scale. The test is repeated twice and an average score is taken for further analysis (Holt et al., 1999).

Skin temperature

Radiofrequency-based therapy at 448kHz in the capacity mode increases skin temperature by around 3°C (Kumaran & Watson, 2015). Skin temperature in the area of the M. erector spinae is measured twice, immediately after the first and last diathermy therapy, using infrared thermal imaging (FLIR A615 series, Emitec Industrial, Rotkreuz, Switzerland) and data analysis software (FLIR ResearchIR Max). Participants are placed on an examination table to receive the diathermy treatment. The camera is installed on top of the examination table to take a picture of the right side of the erector spinae immediately after the treatment without the participant moving.

Rating of perceived effort (RPE-E)

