Training to momentary failure (MF) is considered to be optimal for improving strength. In submaximal efforts, the dose-response relationship for adaptations is not fully clear yet (Steele et al., 2016). The rating of perceived effort (RPE-E) provides a valid and easily accessible measure of exercise intensity in resistance training (Lea et al., 2022). We use the Borg's Category-Ratio-Scale (CR-10) for strength training (Buckley & Borg, 2011) which is based on the original 15-grade Borg's scale for ratings of perceived exertion (Borg, 1982). Immediately after completion of every single of the 12 training sessions on the back extensor machine, the examiner asks the participant "How hard do you think you're working?". The participant reports her/his perceived effort verbally with a number from 0 (no exertion at all) to 10 (maximal effort) orientating on a scale visually.

Rating of perceived discomfort (RPE-D)

Particularly in resistance training it is important to differentiate between the perception of effort (RPE-E) and discomfort (RPE-D) (Steele et al., 2016). Discomfort is the physiological and

unpleasant sensations associated with exercise. Increasing number of repetitions and longer time under muscular tension leads to higher discomfort. Therefore, higher discomfort is experienced in low load than in high load training (Fisher et al., 2018). We use a Category-Ratio-Scale (CR-10) for the RPE-D (Steele et al., 2016). Immediately after the completion of each of the 12 training sessions on the ILEX machine, the participant is asked to report her/his perceived discomfort verbally with a number from 0 (no discomfort) to 10 (maximal discomfort) orientating on a scale visually.

Rating of thermal sensation

Immediately after each of the 12 diathermy treatments, the participant is asked to rate the thermal sensation in the area of the back extensor according to the ISO 10551. The participant rates thermal sensation ("How does this feel like?") using a 9-point Likert scale from 4 (very hot) to -4 (very cold) (Fabbri, 2015).

Rating of perceived comfort

After completion of the rating of thermal sensation, participants are asked to rate the comfort felt during the diathermy treatment on a 5-point scale ranging from 0 "angenehm" to 4 "äusserst unangenehm" (1 "etwas unangenehm", 2 "unangenehm", 3 "sehr unangenehm") (Zhang et al., 2004).

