4 STUDY POPULATION AND STUDY PROCEDURES

4.1 Inclusion and exclusion criteria, justification of study population

Power analysis was conducted with G*power to determine participants numbers (n) calculating a treatment effect size of 0.46 from previous research with the comparable MedX ILEX device in healthy volunteers (Fisher et al., 2018). The priori sample size was calculated ($\alpha = 0.05$; effect size = 0.46; test family = F test, and statistical test = analysis of variance (ANOVA) repeated measures, within-between interaction; number of groups = 2; number of measurements = 3; power = 0.8) and revealed $n = 10$ participants. 14 healthy volunteers will be recruited according to the following criteria:

Study inclusion criteria:

- Healthy (no acute musculoskeletal injuries or illness),
- Pain free,
- Sufficient understanding of the German language,
- Able to give informed consent as documented by signature,
- Between 18 and 50 years old

Study exclusion criteria:

- Pregnant (urine pregnancy test is given to participating woman) or lactating women,
- Medication,
- Previous surgery in the lumbar spine,
- Knee or hip disorders contraindicating the use of ILEX device,
- Currently experiencing LBP,
- History of LBP or lumbar spine pathologies or known deformities,
- Psychological or neuromuscular disorders, spinal pathologies or any other injuries or illness that would restrict normal movement,
- Previous (last 12 months) or current isolated training of the lumbar extensor.

This study will be conducted in healthy people. The risk of injury will be low in this population group.

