5 STATISTICS AND METHODOLOGY

5.1. Statistical analysis plan and sample size calculation

A priori sample size calculation was performed using G*power (Version 3.1, Franz Faul, Germany) to determine participants numbers (n) ($\alpha = 0.05$; effect size = 0.46; test family = F test, and statistical test = analysis of variance (ANOVA) repeated measures, within-between interaction; number of groups = 2; number of measurements = 3; power = 0.8) and revealed n = 10 participants. The effect size was estimated based on previous research with a comparable ILEX device in healthy volunteers (Fisher et al., 2018).

Assumption of normality will be verified using the Shapiro-Wilk test. Mauchly's test will indicate the violation of the assumption of sphericity. Normally distributed data will be analysed applying ANOVA repeated measures with within-between interactions to compare the means of each variable over the three repeated observations (within) and between the intervention and sham group (between). Not normally distributed data will be examined using non-parametric statistics (Friedman's two-way ANOVA). Post hoc Bonferroni test correction will be applied. Probability values $p < 0.05$ will be considered statistically significant.

Men and women are included in this study and will be part of the randomization process. The planned sample size of this study does not allow for gender-specific analysis. A gender difference analysis will have to be part of a future study.

Analyses will be performed using RStudio Team (2023) (RStudio: Integrated Development Environment for R. Boston, MA) and IBM SPSS Statistics (Version 27, IBM Corp., Armonk, NY, USA).

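### Section 5.1's three-observation analysis does not fit five secondary endpoints measured two or twelve times, names no between-arm contrast for them, and its non-normal fallback has none

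*Combined protocol and SAP*

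**What the plan says.** Section 5.1 specifies a repeated-measures ANOVA with within-between interactions to "compare the means of each variable over the three repeated observations (within) and between the intervention and sham group (between"). Mauchly's test checks sphericity. Data that fail the Shapiro-Wilk check go to Friedman's test, and a Bonferroni correction is applied post hoc. The threshold is stated once: "Probability values $p < 0.05$ will be considered statistically significant". The sample size rests on the interaction term: "repeated measures, within-between interaction; number of groups = 2; number of measurements = 3; power = 0.8) and revealed n = 10 participants".

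Section 3.2 lists eight secondary endpoints. Endurance, muscle thickness and lumbar flexibility are measured at baseline, F/U1 and F/U2, as is the primary force endpoint. The other five follow different schedules:

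- Skin temperature "is measured twice, immediately after the first and last diathermy therapy".
- Thermal sensation: "Immediately after each of the 12 diathermy treatments, the participant is asked to rate the thermal sensation". The comfort rating follows each of these.
- Perceived effort: "Immediately after completion of every single of the 12 training sessions on the back extensor machine". Perceived discomfort has the same schedule.

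Appendix 1 agrees, with two marks for skin temperature and twelve for each rating. Section 4.3 has the effort, discomfort and thermal sensation scales shown at the examination visit for familiarisation only. No untreated value is described for any of the five. Neither Section 5.1 nor Section 5.2 says how two or twelve values enter the analysis.

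**The concern.** For an outcome with a pre-treatment value, the group-by-time interaction is the natural test: the arms start level and treatment separates them. For an outcome first observed after treatment, the separation may already be there at the first observation. The interaction then asks only whether the gap changes from session to session. The relevant contrast is the overall difference between arms, and Section 5.1 does not say so.

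The rationale of the trial is deep-tissue heating, and the documents describe no measurement of muscle temperature. Skin temperature and thermal sensation are therefore the available evidence that the active arm was warmed and the sham arm was not. The effort and discomfort ratings show whether training felt the same in both arms. If the contrast is left open, it is chosen after the data are seen. If the ratings go to the non-normal route, the stated test makes no comparison between arms.

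**Working it through.** **1. The plan's own figure.** Inputs from Section 5.1: "effect size = 0.46; test family = F test", alpha 0.05, 2 groups, 3 measurements, power 0.80. Not stated and therefore assumed: correlation rho = 0.5 and epsilon = 1, with 0.46 read as Cohen's f in the G*Power default parameterisation.

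- lambda = f² × N × m / (1 − rho) = 0.2116 × 10 × 3 / 0.5 = 12.70
- df1 = (2 − 1)(3 − 1) = 2; df2 = (10 − 2)(3 − 1) = 16
- Power = 0.833 at N = 10 and 0.709 at N = 8

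The stated n = 10 is reproduced, and it is a calculation for the interaction with three measurements. At N = 14 the same formula gives 0.952. None of this bears on outcomes with two or twelve values and no baseline.

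**2. Observation counts.**

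| Endpoint | Observations | Untreated value |
|---|---|---|
| Force, endurance, thickness, flexibility/ROM | 3 | yes (BL) |
| Skin temperature | 2 | none described |
| Effort, discomfort, thermal sensation, comfort | 12 each | none described |

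**3. Which term carries a constant arm difference.** Section 4.1 gives the total: "14 healthy volunteers will be recruited according to the following criteria". The allocation ratio is not stated, so 7 per arm is assumed. Also assumed: compound symmetry with rho 0.3 to 0.7, and a difference of d SD that is the same at every observation. There were 10,000 simulated trials per setting.

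| m | d (SD) | Interaction rejects | Group effect rejects | Friedman, arms pooled |
|---|---|---|---|---|
| 2 | 1 | 4.6% to 5.3% | 47% to 57% | 5.5% to 5.8% |
| 2 | 2 | 4.9% to 5.3% | 96% to 99% | 5.5% to 5.9% |
| 12 | 1 | 4.8% to 4.9% | 52% to 83% | 4.2% to 4.4% |
| 12 | 2 | 4.8% to 5.1% | 98% to 100% | 4.3% to 4.4% |

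The interaction and Friedman columns stay near alpha by construction: with no change over time, neither statistic has anything to detect. At d = 3 the group effect rejects in essentially every trial.

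Analytic check of the group column: a participant mean has variance rho + (1 − rho)/m, and the noncentrality is d × √(7/2) / √variance on 12 df. For m = 2, rho = 0.5, d = 1 the variance is 0.75, the noncentrality is 1.871/0.866 = 2.16, and power is 51%, which agrees with the simulated 50.8%.

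As an illustration in degrees, Section 3.2 cites a rise of about 3 °C after radiofrequency. If that were the whole arm difference, and the SD were 1 to 2 °C (d = 3 to 1.5) with rho = 0.5, the group effect would reject in 84% to 100% of trials.

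**4. The non-normal route.** Friedman's test ranks each participant's own values across sessions. Adding a constant to everyone in one arm leaves every rank unchanged. Run on pooled data or within each arm, it contains no comparison between arms.

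**5. Twelve levels in 14 people.** Under the Withdrawal and discontinuation heading in Section 4.3, missed sessions are expected and judged case by case. A classical repeated-measures ANOVA uses complete cases. If each session is missed independently with an assumed probability of 2%, 0.98¹² = 0.785 of participants are complete, or 11.0 of 14. At 5%, 0.95¹² = 0.540, or 7.6 of 14. Mauchly's test on 12 levels involves 11 contrasts and needs N − 2 ≥ 11, so N ≥ 13. It cannot be computed once two of the 14 are lost.

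**The case against.** The strongest reply is that the stated model already holds the right test. A two-group repeated-measures ANOVA has terms for time, group and their product, and the sentence in Section 5.1 explicitly includes the comparison of intervention with sham. With complete data, the group F statistic equals the squared equal-variance t statistic on participant means. A reader might infer that the interaction is the only analysis, so that a steady heating difference goes untested. On the ANOVA route the documents do not support that, and nothing in Section 5.1 limits reporting to the interaction.

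A reader might also infer that the primary result loses its manipulation check. The documents never give these endpoints that label, the hypotheses in Section 3.1 do not cover them, and the primary endpoint has a baseline and three observations.

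The inputs are open to challenge too. The 3 °C figure is a rise after radiofrequency, not a difference from a sham that includes massage with the device. The SDs, the effect sizes and the missed-session rates are assumed. A diathermy effect need not be constant: ratings could adapt over twelve sessions, and then an interaction would be informative.

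All of this stands. What it leaves untouched is the mismatch in observation counts, the unnamed contrast, the lack of a between-arm term in the fallback, and the complete-case problem with twelve levels. Section 4.3 says data already collected are to be used as far as possible, but gives no method for doing so with incomplete sessions.

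**Conclusion.** The point holds as a defect in the analysis of five secondary endpoints. The three-observation rule cannot be applied to them as written, and Section 5.1 does not say that the group main effect is what matters there. On the ANOVA route the test exists but is not designated. On the Friedman route an arm difference is not tested at all, and that route is plausible for 5-, 9- and 11-point ratings with about 7 people per arm.

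The observation counts, the invariance of Friedman's test and the limit of 13 participants for Mauchly's test follow from the design. The rejection rates and the 11.0 or 7.6 complete participants are illustrations that rest on the assumptions stated with them. The analysis of the primary endpoint is unaffected; only the supporting evidence used to interpret it is at issue.

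**What to change.** In Section 5.1:

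- Limit the three-observation ANOVA to outcomes measured at BL, F/U1 and F/U2.
- For skin temperature, use each participant's mean of the two images. For perceived effort, perceived discomfort, thermal sensation and comfort, use each participant's mean over attended sessions.
- Compare arms on these means, reporting the difference with a 95% CI. For the four ratings, use a rank-sum or permutation test in place of Friedman.
- Report change across sessions as a secondary description.

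The participant mean keeps people who missed some sessions and needs no sphericity test. The cost is SAP wording only, with no new data. The one drawback is that averaging hides change from the first session to the last, so the session-by-session course should still be shown by arm.

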3 STUDY OBJECTIVES AND DESIGN

3.1 Hypothesis and primary objective

The main aim of this study is to investigate the effect of back extensor strength after 6 weeks of ILEX training and diathermy therapy.

- H_0 : 6 weeks of resistance training on the ILEX machine does not improve lumbar extensor muscle strength.
- H_1 : 6 weeks of resistance training on the ILEX machine improves the strength of the lumbar extensor muscle.
- H_0 : There is no difference in the improvement in lumbar extensor muscle strength between those who receive a microwave diathermy treatment before each resistance training session and those in the sham group.
- H_1 : Individuals who receive a microwave diathermy treatment prior to each resistance training session improve their lumbar extensor muscle strength more than those in the sham group.

Secondary objectives are to examine the development of M. erector spinae thickness, isometric back extension endurance, and lumbar extensor flexibility after 6 weeks of resistance training and diathermy therapy.

- H_0 : 6 weeks of resistance training on the ILEX machine does not enhance the thickness of the M. erector spinae.
- H_1 : 6 weeks of resistance training on the ILEX machine enhances the thickness of the M. erector spinae.
- H_0 : There is no difference in the increase of the thickness of the M. erector spinae between those who receive a microwave diathermy treatment before each resistance training session and those in the sham group.
- H_1 : Individuals who receive a microwave diathermy treatment prior to each resistance training session enhance the thickness of the M. erector spinae more than those in the sham group.
- H_0 : 6 weeks of resistance training on the ILEX machine does not improve isometric back extension strength endurance.

- H_1 : 6 weeks of resistance training on the ILEX machine improves isometric back extension strength endurance.
- H_0 : There is no difference in the improvement of the isometric back extension strength endurance between those who receive a microwave diathermy treatment before each resistance training session and those in the sham group.
- H_1 : Individuals who receive a microwave diathermy treatment prior to each resistance training session improve the isometric back extension strength endurance more than those in the sham group.
- H_0 : 6 weeks of resistance training on the ILEX machine does not increase lumbar ROM.
- H_1 : 6 weeks of resistance training on the ILEX machine increases lumbar ROM.

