- H_0 : There is no difference in the increase of the lumbar ROM between those who receive a microwave diathermy treatment before each resistance training session and those in the sham group.
- H_1 : Individuals who receive a microwave diathermy treatment prior to each resistance training session increase of the lumbar ROM more than those in the sham group.

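### For non-normal outcomes the plan names only Friedman's test, which has no group term, so diathermy versus sham then has no prespecified test

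*Combined protocol and SAP*

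**What the plan says.** Section 3.1 gives each outcome two separate hypotheses. One concerns training: for strength, that "6 weeks of resistance training on the ILEX machine improves the strength of the lumbar extensor muscle". The other concerns diathermy, and it is stated four times. Treated participants are expected to:

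- "improve their lumbar extensor muscle strength more than those in the sham group" (primary outcome);
- "enhance the thickness of the M. erector spinae more than those in the sham group";
- "improve the isometric back extension strength endurance more than those in the sham group";
- "increase of the lumbar ROM more than those in the sham group".

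Section 5.1 then sets two analysis routes and a switch between them. The switch is: "Assumption of normality will be verified using the Shapiro-Wilk test". Normal data go to "ANOVA repeated measures with within-between interactions", described as comparing the three visits (within) and intervention with sham (between). For the other route the text is: "Not normally distributed data will be examined using non-parametric statistics (Friedman's two-way ANOVA". A Bonferroni post hoc correction and a 0.05 significance level complete the paragraph. No other section names a non-parametric comparison of the two arms.

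**The concern.** The comparison of arms is written into the first route and is absent from the second. The two ways in Friedman's two-way ANOVA are participant and visit; treatment group is not one of them. If an outcome is sent down the second route, its training hypothesis keeps a valid test and its diathermy hypothesis has none.

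This can happen to the primary outcome. The randomisation and the sham arm described in section 3.3 exist to answer the diathermy question. With no planned test for it, the team would have to choose one after seeing the data, or a significant change over time could be taken as support for diathermy.

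**Working it through.** **1. Routes against hypotheses (sections 3.1 and 5.1)**

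| Hypothesis | Normal data | Non-normal data |
|---|---|---|
| Training changes the outcome | ANOVA, time effect | Friedman |
| Diathermy beats sham | ANOVA, group-by-time interaction | nothing named |

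**2. Friedman's statistic.** With n participants, k visits and R_j the sum over participants of the within-participant ranks at visit j:

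Q = 12 / [n k (k+1)] × ΣR_j² − 3n(k+1).

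With n = 14 (section 4.1) and k = 3, Q = ΣR_j² / 14 − 168. Group does not enter. In one simulated data set Q was 0.143 (p = 0.931). Adding 100 to every value in one arm left it at 0.143, and so did shuffling the group labels.

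**3. The plan's own sample size rests on the interaction.** Inputs from section 5.1: f = 0.46, two groups, three measurements, alpha 0.05, power 0.8. Assumed because not given: correlation 0.5, sphericity 1. The noncentrality is λ = f² × N × 3 / (1 − 0.5).

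- N = 10: λ = 0.2116 × 10 × 3 / 0.5 = 12.7, df 2 and 16, power 0.833.
- N = 8: power 0.709.

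The stated n = 10 therefore reproduces and is not in dispute. It shows that the trial was sized for the very comparison the fallback omits.

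**4. What Friedman responds to.** Simulation with assumptions that are not in the documents: 7 per arm, unit SD, equal correlation between visits, linear gain, normal data.

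*No diathermy effect* (both arms gain equally), share of trials significant:

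| Training gain | Friedman, corr. 0.5 | Friedman, corr. 0.8 |
|---|---|---|
| 0.5 SD | 25% | 55% |
| 1.0 SD | 78% | 99% |

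These figures are power for the training hypothesis, not false-positive rates. Under the same conditions a Mann-Whitney test on baseline to F/U2 change rejects in 3-4% and a permuted interaction F in 4-5%.

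*Diathermy adds 1 SD of gain.* Mann-Whitney rejects in 33-34% (correlation 0.5) and 71% (0.8); the permuted F in 32% and 69%. Friedman's response depends on how the effect is added. With the mean gain of the two arms held at 0.5 SD, so that sham gains nothing, it falls from 25% to 21% and from 55% to 35%. With the sham gain held at 0.5 SD, it rises from 25% to 69% and from 55% to 95%. It follows the average change, not the difference between arms.

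*The plan's own effect.* For a linear interaction f = 0.204 × the difference in gain, so 0.46 means 0.46 / 0.204 ≈ 2.25 SD. With no average gain and correlation 0.5, Friedman rejects in 1% of trials and Mann-Whitney on change in 95%.

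**5. How often the fallback would fire.** This depends on what Shapiro-Wilk is applied to, which is not stated. If tests were independent, three pooled visits would give 1 − 0.95³ = 14% and six arm-by-visit cells 1 − 0.95⁶ = 26%. Simulated rates per outcome at 0.05:

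| Shapiro-Wilk applied to | Truly normal data (corr. 0.5-0.9) | Log-normal data, log-SD 0.75 |
|---|---|---|
| Residuals of change scores | 4-5% | 28-31% |
| Three pooled visits | 12-14% | 81-93% |
| Six arm-by-visit cells | 24-27% | 71-84% |

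The last column rests on a single assumed, strong skew (coefficient of variation about 87%). It does not predict how strength will behave in this population.

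**The case against.** - *The gap is conditional.* Section 5.1 does test the group-by-time interaction when data pass Shapiro-Wilk, and nothing in the documents suggests that strength is non-normal. This stands and limits the severity. But the switch can fire by chance on normal data, and it applies separately to four outcomes.
- *Friedman may be only an example of a non-parametric method.* Even so, no other test is named, so none is prespecified.
- *Bonferroni post hoc tests could supply the comparison.* That sentence names a correction and no comparison. Post hoc tests after Friedman compare visits, not arms.
- *Friedman could be run in each arm and the results compared.* The plan does not say so, and it would not be a valid comparison. With equal true gains of 1.0 SD and correlation 0.5, the two arms disagreed on significance in 50% of simulated trials.
- *The interaction F could simply be kept whatever Shapiro-Wilk shows.* This is a reasonable alternative. In the skewed setting above its type I error was 3.5-3.8%. With 1 SD added by diathermy its power was 39-40% (correlation 0.5) and 69-70% (0.8), against 44% and 73% for the permuted F and 50-51% and 78-79% for Mann-Whitney. The choice of remedy is partly preference, but the plan has not made any choice.
- *Section 3.1 keeps the training and diathermy hypotheses apart, so misreading is speculative.* This is fair. The main harm is the missing test.

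**Conclusion.** The concern holds. Under the rule in section 5.1, any of the four outcomes judged non-normal, primary strength included, loses its only planned test of diathermy against sham. That conclusion follows from the form of Friedman's statistic and needs no simulation.

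The size of the problem is conditional. It depends on how often the fallback fires, which the plan leaves undefined: roughly 4-5% to 24-27% per outcome on normal data, and more if the data are skewed. All simulated rates assume 7 per arm and the stated correlations, and they are illustrations only. The ANOVA route, the sample size and the use of Friedman for change over time are not faulted. The text should be corrected before outcomes are examined by arm.

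**What to change.** In section 5.1, keep the repeated-measures ANOVA interaction as the main analysis and add three statements.

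1. For non-normal outcomes the diathermy-versus-sham hypothesis is tested by one named method. Either (a) permute group labels within sex strata and recompute the planned interaction F, reading direction from the difference in baseline to F/U2 gain; or (b) use a sex-stratified Wilcoxon-Mann-Whitney test on the baseline to F/U2 change.
2. Friedman's test serves only the change-over-time hypotheses and is not evidence for or against diathermy.
3. The quantity to which Shapiro-Wilk is applied is stated, for example the residuals of the change scores.

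The cost is two or three sentences. R, already named in section 5.1, runs either test, and no data or participants are added. The change may need submission to the Ethics Committee under section 6.6.

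Option (b) ignores F/U1. The Mann-Whitney figures above are unstratified; a stratified check gave similar results (about 5% size, 34% and 71% power). Option (a) must follow the actual block scheme, whose block size section 3.3 does not give. The 5% level stays reachable: an assumed split of 4 and 3 by sex in each arm gives C(8,4) × C(6,3) = 70 × 20 = 1,400 relabellings, and even seven blocks of two give 2⁷ = 128, with a smallest p of 2/128 = 0.016.

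### Section 5.1 names no between-arm contrast, visit, estimate or confidence interval for diathermy versus sham, so with about 7 per arm a non-significant test would not by itself support a conclusion of no difference.

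*Combined protocol and SAP*

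**What the plan says.** Section 5.1 holds the whole analysis plan. After checks of normality and sphericity, a repeated-measures ANOVA with within-between interaction is used "to compare the means of each variable over the three repeated observations (within) and between the intervention and sham group (between"). Friedman's test replaces it for non-normal data, a Bonferroni post hoc correction follows, and p-values below 0.05 "will be considered statistically significant".

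The sample size rests on the same test: "test family = F test, and statistical test = analysis of variance (ANOVA) repeated measures, within-between interaction", with an effect size of 0.46 and "number of groups = 2; number of measurements = 3; power = 0.8) and revealed n = 10 participants". Section 4.1 then sets recruitment: "14 healthy volunteers will be recruited according to the following criteria".

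The between-arm null for the primary endpoint in section 3.1 begins: "There is no difference in the improvement in lumbar extensor muscle strength between those who receive". Its alternative is directional: the diathermy group gains more strength than the sham group.

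No section plans a diathermy-minus-sham difference, a reported effect size or a confidence interval. Effect size appears only as a sample-size input. Maximal isometric force is measured at BL, F/U1 and F/U2 (sections 3.2 and 3.4), but the baseline value is not planned as a covariate.

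**The concern.** The question is whether preheating adds strength, and by how much. With two groups and three measurements the interaction F has (2−1)(3−1) = 2 numerator degrees of freedom. It tests whether the arms' profiles differ in any way over the three visits. It has no direction, no size in the endpoint's unit, and can be significant because the arms part at F/U1 alone. The post hoc step could supply comparisons of means, but the plan does not say which pairs or which visit, so that choice stays open until the data are seen. The Friedman fallback provides no between-arm estimate either.

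In a trial of 14 people the estimate and its interval are the main information available. Without them a significant result has no size attached, and a non-significant one gives no indication of which differences remain possible. Section 7.1 expects the results to guide patients and announces later patient studies, which would need both.

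**Working it through.** **Inputs.** From the documents: alpha 0.05, effect size 0.46 (read as Cohen's f), 2 groups, 3 measurements, power 0.80, n = 10 (section 5.1); 14 recruited (section 4.1); drop-outs not replaced (section 5.2). Assumed: 7 per arm, since no allocation ratio is given; correlation between visits ρ = 0.5 and sphericity for the sample-size check, since neither is stated.

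**1. The plan's own figure.** Noncentrality λ = f² × N × m / (1 − ρ), with df 2 and 2(N − 2).
- N = 10: λ = 0.2116 × 10 × 3 / 0.5 = 12.70, power 0.833.
- N = 8: power 0.709. So 10 is the smallest even N reaching 0.80, and the stated n reproduces.
- N = 14: power 0.952.
- The result depends on ρ: N = 18 at ρ = 0, 14 at 0.3, 8 at 0.7.

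**2. What f = 0.46 means.** If the arms diverge linearly over the three visits, the difference at F/U2 is 4a with f = a√(2/3). So 4a = 4 × 0.46 × √1.5 = 2.25 raw SD. The SD of change is √(2(1 − ρ)) = 1 raw SD at ρ = 0.5, so the planning effect is about 2.25 SD of change.

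**3. Interval width.** Half-width for the difference in BL-to-F/U2 change, in SD of change: t(0.975; n₁ + n₂ − 2) × √(1/n₁ + 1/n₂).
- 7 per arm: 2.179 × √(2/7) = 1.16
- 8 and 6: 1.18
- 6 per arm: 1.29
- 5 per arm: 2.306 × √(2/5) = 1.46

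An observed difference of exactly zero at 7 per arm gives −1.16 to +1.16 SD.

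**4. Chance of p ≥ 0.05 when the true difference is 1 SD of change, 7 per arm.**
- Planned interaction F, linear divergence: at ρ = 0.5, 4a = 1 gives a = 0.25 and f = 0.204, so λ = 0.0417 × 14 × 3 / 0.5 = 3.5 on 2 and 24 df. Power is 0.33, so about 67% are non-significant.
- Two-sample t test on change: noncentrality 1 × √(7/2) = 1.87 on 12 df. Power is 0.41, so 59% are non-significant. At true differences of 0.8 and 1.2 SD the figures are 72% and 46%.

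The squared t noncentrality, 1.87² = 3.5, equals λ. The information is the same, but the F spreads it over two degrees of freedom.

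**5. Baseline-adjusted F/U2 contrast** (simulated, 7 per arm; half-widths are means, in raw-score SD; power is for a true difference of 1 SD of change, linear divergence).

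| BL–F/U2 correlation | Half-width, change score | Half-width, adjusted | Power, adjusted |
|---|---|---|---|
| 0.3 | 1.35 | 1.15 | about 0.53 |
| 0.5 | 1.14 | 1.04 | about 0.48 |
| 0.8 | 0.72 | 0.72 | about 0.40 |
| 0.9 | 0.51 | 0.52 | about 0.38 |

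The planned F has power of about 0.33 for the same effect. The documents give no correlation, so this is a range.

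**The case against.** A reader might infer that a p-value is the only planned output. The text does not support that: section 5.1 says means will be compared and adds corrected post hoc tests, and any ANOVA software will print group means. What is missing is narrower: which contrast, at which visit, with what interval.

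A reader might also infer that the plan commits the sponsor to declaring no effect when p ≥ 0.05. It does not. The null in section 3.1 is ordinary null-hypothesis wording, and how a null result would be read is a forecast.

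Three points on size also stand in part.
- The trial is not weak against its own planning effect. An observed difference near zero would exclude 2.25 SD of change, so such a null is not empty. It would still not exclude differences of about 1 SD.
- Whether 1 SD stays open depends on the result. In the direction of benefit, the upper limit falls below 1 SD once the observed difference is below about −0.16 SD (−0.16 + 1.16 = 1.00). A one-sided 95% bound at zero would be 0.95 SD, but the planned F is not one-sided.
- One SD of change is not tied to an important difference in force. The documents give no SD, so the width cannot be put in newtons.

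Finally, baseline adjustment brings little where visits correlate highly. That is true of the interval (0.8 and above), and it is a cost to state. The gain in power over the 2-df F remains across the range examined.

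**Conclusion.** The point holds as a gap in the specified analysis and reporting. The plan tests a directional hypothesis with a non-directional 2-df F and prespecifies no contrast, visit, estimate or interval. With 7 per arm the 95% half-width is about 1.16 SD of change (1.46 at 5 per arm). A true 1 SD difference would be missed in about 67% of trials with the planned F, or 59% with a t test on change. A non-significant result would thus not by itself support the null.

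This rests on an inferred equal split, on linear divergence for the F figure, and on a two-sided 95% level. Seven per arm is the best case: an unequal split, drop-out or a Bonferroni adjustment widens the interval. The finding does not show that the sample size was miscalculated, since n = 10 reproduces with ρ = 0.5. The change should be made before the data are analysed; it is no obstacle to running the trial.

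**What to change.** In section 5.1, state that:

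1. The primary diathermy effect is the between-arm difference in maximal isometric force at F/U2, from a model with arm and baseline force, reported in the endpoint's unit with its 95% confidence interval.
2. The p-value from this same model governs the diathermy hypothesis, and the repeated-measures interaction is supportive. One of them must be named: in simulation at a true 1 SD difference, the two disagreed on significance in 26%, 19% and 18% of trials at correlations of 0.5, 0.8 and 0.9.
3. A result with p ≥ 0.05 is reported as inconclusive over the range of the interval.

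Apply the same model to the secondary endpoints measured at BL and F/U2: erector spinae thickness, isometric back extension endurance, ROM and sit-and-reach. It does not carry over to the session ratings or skin temperature, which have no matching baseline and follow-up pair.

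The cost is SAP wording and a few lines of output, with no extra data, visits or participants. One degree of freedom goes to baseline, and at a BL–F/U2 correlation of 0.8 or above the interval narrows little or not at all against change scores (marginally wider at 0.9). Null results must be worded more cautiously.
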